Title: “Acute effects of spinal manipulation on sports performance in amateur cyclists. Pilot study”

Title (spanish): “Efectos agudos de la manipulación espinal en el rendimiento deportivo en ciclistas amateur. Estudio piloto”

Date: January, 14 2019

Introduction

Spinal manipulative therapy (SMT), which consists on the application of high-speed, low-amplitude movements, slightly above the range of passive movement of the spinal joints (Bronfort, Haas, Evans, & Bouter, 2004), is widely used for the treatment of various musculoskeletal conditions such as acute or chronic back pain, having shown that it provides benefits both in terms of pain and function (Bronfort et al., 2004; Gross et al., 2015; Paige et al., 2017).

The use of the SMT is also expanding to the sports field, being used by many athletes before their competitions, trusting in a potential ergogenic effect. In fact, greater corticospinal excitability and greater electromyographic activity have been observed acutely after a single session of SMT (Christiansen et al., 2018; Niazi et al., 2015), effects that could result in greater muscle strength and ultimately in better sports performance.

However, the evidence regarding the benefits of SMT in performance is scant and contradictory. Some studies have observed greater muscular strength both in subjects with spinal dysfunction (Niazi et al., 2015) and in elite athletes (Botelho & Andrade, 2012; Christiansen et al., 2018). On the contrary, others did not find benefits in muscle force (Humphries et al., 2013; Sanders et al., 2015). Neither have benefits been observed in a running incremental test (Ward et al., 2012) or in other specific sports actions such as jumping or sprinting (Shrier, Macdonald, & Uchacz, 2006). Therefore, there is still not enough evidence to support the ergogenic role of this technique for the acute improvement of sports performance.

In a recently published study, an increase in parasympathetic modulation of the autonomic nervous system was found after performing SMT with Activator throughout the entire spine (at the discretion of the chiropractic specialist) (Valenzuela, Pancorbo, Lucia, & Germain, 2018). However, no acute benefits in performance were observed. Given these results, we hypothesized that the absence of such benefits could be due to the global manipulation of the spine, instead of a specific action on the segments related to the dorsal roots that innervate the lower limbs. The aim of the present project is to verify if SMT performed on the dorsal roots of the lumbar segments is able to enhance the neuromuscular performance of the lower limbs in amateur cyclists.

Hypothesis

Our hypothesis is that SMT performed on the dorsal roots of the lumbar segments is able to improve neuromuscular performance, improving the maximum force, power or muscle activation, or at least reducing the perceived effort to achieve the same performance.

Objectives

- General objective: To determine the effects of SMT on neuromuscular performance in athletes.
- Specific objective: To determine the effects of SMT on muscle strength, voluntary activation and power.

Methodology

Participants

In this pilot study we will try to include 40 participants. Participants will be recruited from local sports clubs. The inclusion criteria will be: being male between 18 and 45 years old, training a minimum of 3 hours per week, and not having received SMT in at least one year. The exclusion criteria will be: having suffered an injury or illness during the two months prior to the test, or having been unable to maintain the usual training rhythm during the previous month. Prior to their participation, the subjects must sign an informed consent form after reading the corresponding information sheet of the study.

Experimental design

The present study will follow a randomized, double-blind (participant and assessor), parallel and sham-controlled design. Participants must attend to the facilities twice; and these visits will be separated by 7 days. Subjects will be randomly assigned to receive the actual SMT intervention or a sham intervention. Once randomized, all participants will make a first control visit in which the tests will be carried out without receiving any type of intervention. At the second visit, the corresponding treatment (real or sham) will be applied before the tests. Each subject will perform the tests at the same time of day. Participants should maintain their eating habits during the experimental period, as well

as to avoid caffeine consumption and physical exercise in the 48 hours prior to each visit.

Measurements

The descriptive and anthropometric variables of the athletes will be measured by means of a scale and a stadiometer. We will also ask participants about the number of hours that they usually train per week.

Subsequently, participants will perform an isometric maximum voluntary contraction (MVC) with the knee extensors. Specifically, they will perform three 5-second repetitions with the dominant leg, and the maximum force attained will be measured by means of a handheld dynamometer (microFET®2, Hoggan Scientific). The highest force reached in these contractions will be used for analysis. In addition, the maximum activation level of the vastus lateralis muscle will be also assessed by means of surface electromyography (ML856 PowerLab 26T, LabChart, ADInstruments, New Zealand) during these MVCs.

Muscle power and overall ‘anaerobic’ performance will be assessed by means of the Wingate test, performed on a cycle ergometer with electromagnetic brake (CardiGyrus Medical, Bikemac, Sabadell, Spain). This test, one of the most popular for the evaluation of anaerobic power (Driss & Vandewalle, 2013), will last 30 seconds. Participants should try to achieve the maximum possible power during the test. We will analyze both the peak power (greatest power reached in periods of 1 second) and the mean power attained during the test. In addition, immediately after the test we will assess the rating of perceived exertion on a 1-10 scale (Borg, 1998).

Intervention

The actual SMT intervention will always be performed by a chiropractic specialist, while the placebo intervention will be performed by the other chiropractor. The actual SMT intervention will consist of spinal manipulation with high velocity and low amplitude movements. Participants will be evaluated according to the basic Activator protocol (Fuhr, 2005). This protocol consists of the visual evaluation of possible differences in the length of the legs by performing maneuvers with the participant in prone position. These maneuvers are performed to locate the spinal areas that may present a possible dysfunction, applying a manipulation in these areas with the

Activator instrument (AAI IV, Activator Methods International, Ltd, Phoenix, AZ). This instrument will allow us to exert the same pressure on all subjects. In the actual SMT intervention the Activator will be placed in the force position 4, which exerts a pressure of very short duration (5 ms) and a force peak of approximately 176 N.

In the sham SMT condition all the maneuvers and evaluations will be carried out as in the actual SMT one. However, the Activator will be placed in the 0-force position, which means that the instrument will generate noise, but practically no movement will occur (approximately 19.5 N). Neither in the sham nor in the actual SMT intervention there are physical or mental risks for the participant, which is why they are considered non-invasive procedures.

Although the chiropractors who administer the interventions (real SMT or placebo) will know the condition assigned to each participant, the latter and the researchers in charge of the outcomes assessment and of the statistical analysis will remain blind to this information. As it is not a cross-over study (each participant is tested after only one condition, actual or sham SMT), the participants will not know the real pressure that the Activator instrument exerts. Therefore, all participants will believe that they are receiving the actual SMT intervention.

Statistical analysis

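### The areas to treat are chosen by eye by chiropractors who very probably know the arm, and nothing protects or verifies the match between real and sham sessions

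*Combined protocol and SAP*

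**What the plan says.** All references are to the combined protocol and SAP.

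- **Who is blind.** Experimental design describes a "randomized, double-blind (participant and assessor), parallel and sham-controlled design". The Intervention section adds the statistical analysts to those kept blind and says plainly that the operators are not: "Although the chiropractors who administer the interventions (real SMT or placebo) will know the condition assigned to each participant".
- **Who treats.** Real SMT will "always be performed by a chiropractic specialist, while the placebo intervention will be performed by the other chiropractor".
- **How areas are found.** The evaluation is a "visual evaluation of possible differences in the length of the legs by performing maneuvers with the participant in prone position". Its purpose is stated: "These maneuvers are performed to locate the spinal areas that may present a possible dysfunction". The Activator is then applied in the areas found.
- **How the sham is matched.** "In the sham SMT condition all the maneuvers and evaluations will be carried out as in the actual SMT one". The same instrument is used and still makes its noise. The planned difference is in force: the real setting "exerts a pressure of very short duration (5 ms) and a force peak of approximately 176 N", and the sham setting gives about 19.5 N.
- **Analysis.** Statistical analysis specifies a two-way ANOVA (intervention by time), with a log transformation and then a Friedman test as fallbacks.

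**The concern.** The evaluation is a subjective judgement, and its result decides where the instrument is applied and in how many areas. It can also affect how many clicks the participant hears and how long he is handled. A chiropractor who knows that the application will be a sham may, without meaning to, search less, find fewer areas or finish sooner. The instruction to perform the same maneuvers can fix which steps are done. It cannot ensure that a judgement made with knowledge of the arm comes out as it would have done without it.

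Two features make this relevant here. First, maximal voluntary contraction, Wingate power and perceived exertion depend on voluntary effort or self-report, so unequal attention or session length could move them. Second, the plan attributes the lack of performance benefit in an earlier study to treating the whole spine instead of specific segments. By its own reasoning the place of application matters, yet that choice is open to influence from the arm.

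The operator must know the arm when the instrument is set. The plan gives no reason why it must be known while the areas are being chosen.

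**Working it through.** **Step 1. When is the arm known?** The plan gives no time of disclosure, and it describes the evaluation in the passive without naming the evaluator. Two statements bear on it:

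- Participants are randomized before the first visit, and treatment is given at the second, 7 days later. The allocation therefore exists well before the evaluation.
- One chiropractor gives all real SMT and the other all sham. If the treating chiropractor does the evaluation, he or she knows the arm on meeting the participant.

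Knowledge of the arm during site selection is thus a strong inference, not stated text.

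**Step 2. What protects the match?**

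| Element | What the plan provides |
|---|---|
| Maneuvers and evaluations | Same in both arms, by instruction |
| Force per application | Set by the instrument |
| Which areas, and how many | Left to the visual judgement; not fixed, no record planned |
| Number of applications | Not fixed, no record planned |
| Contact time | Not fixed, no record planned |
| Check that sessions were alike | None described |

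**Step 3. Can the analysis separate the two sources?** With two arms and two times, the interaction estimates

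(mean change, real) − (mean change, sham).

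If the thrust effect is τ and the effect of unequal handling is b, the expected value is τ + b. The model has no term for areas, applications, contact time or operator, so τ and b cannot be told apart. The Friedman fallback does not separate them either.

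**Step 4. Illustration of size.** The plan has no figure to reproduce: it gives 40 participants without an effect size, SD or power. Inputs:

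- 40 participants (Participants section). Equal arms of 20 are assumed, since no allocation ratio is given.
- Significance level 0.05 (Statistical analysis). Two-sided is assumed.
- τ = 0, and b = d × SD of the change. The values of d are assumed.

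The interaction test is then a two-sample t test on the change, with 20 + 20 − 2 = 38 degrees of freedom and critical value 2.024 (the 97.5% point of t with 38 df). The noncentrality is λ = d × √(20 × 20 / 40) = d × √10. With F the noncentral t distribution function,

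rejection rate = 1 − F(2.024; 38, λ) + F(−2.024; 38, λ).

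| d (SD) | λ | Chance of p < 0.05, per outcome |
|---|---|---|
| 0 | 0 | 5.0% |
| 0.1 | 0.316 | 6.1% |
| 0.2 | 0.632 | 9.5% |
| 0.3 | 0.949 | 15.2% |
| 0.5 | 1.581 | 33.8% |

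These figures show what a given shift would do. They say nothing about whether one occurs, and any bias of that size in a trial of this size would give the same rates.

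**The case against.** The strongest reply is that the plan already answers the point. It requires the same maneuvers and evaluations in the sham, keeps the instrument and its noise, and discloses that operators are unblinded, which is hard to avoid when the operator sets the force. Participants, assessors and analysts are blind. Each participant experiences one condition only and has had no SMT for at least a year, so he has little against which to compare a shorter session. For harm to follow, the search must differ by arm, that difference must reach the participant, and it must then change his effort. The documents contain no data on any of these links. The trial is also a self-described pilot.

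Much of this stands. A reader might infer that the sham is not a matched control. The documents do not support that: the match is specified, and force is the planned procedural difference. A reader might also take it as stated that the chiropractor knows the arm before evaluating, but the timing is not given. A further temptation is to say that comparisons by treated area would be biased, but Statistical analysis plans no such comparison.

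What does not stand is the step from instruction to assurance. Participant blinding does not stop the operator's judgement from differing by arm, and without records nobody could show afterwards that it did not.

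**Conclusion.** The concern holds in a limited form. The sham is matched on paper, but the match in areas, number of applications and contact time is neither protected from knowledge of the arm nor open to verification. The planned analysis would credit any resulting difference to the thrust. This rests on the inference that the treating chiropractor evaluates his or her own participant and knows the arm by then.

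The size is unknown. Under the stated assumptions, the false-positive rate per outcome runs from 5.0% with no shift, through 6.1% at 0.1 SD, to 33.8% at 0.5 SD. The documents give no basis for choosing a value in that range. The change below is worth making because it is cheap and closes an avoidable route for bias, not because bias has been shown.

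**What to change.** In the Intervention section:

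1. Conceal the allocation from both chiropractors until visit 2.
2. At visit 2, the chiropractor seeing the participant performs the maneuvers and writes down the areas.
3. Only then is the sealed allocation opened, out of sight of participant and assessor, and the Activator set to the assigned position.
4. The same chiropractor applies it at exactly the listed areas, so nobody changes practitioner mid-session.
5. Both chiropractors treat both arms, on a schedule unrelated to arm. This also removes the complete overlap of operator with arm, which no analysis could undo.
6. Record areas, number of applications and contact time for each participant, and report them by arm. The operator still knows the arm during application, so the record is needed even with steps 1 to 5.

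The cost is one record sheet and one sealed envelope per participant, a change in the order of steps, slightly more coordination at visit 2, and giving up the rule of one chiropractor per arm. No extra visit or test is needed.

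Two assumptions should be confirmed by the sponsor: that either chiropractor can deliver either arm, and that all areas can be located before the first application. The plan states neither.
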